6.5.1.2. Dose Modifications for Non-hematologic Toxicity

For any non-hematologic toxicity of Grade ≥ 3 severity that persists despite optimal medical treatment, withhold treatment with lerociclib until symptoms resolve to Grade ≤ 2 severity (if not considered a safety risk for the participant). If the treatment interruption duration is > 14 days, approval from the Medical Monitor will be needed to resume treatment.

Treatment should be resumed at the next-lower dose level of lerociclib. If no further dose reduction is possible (participant is already receiving the lowest dose), lerociclib treatment must be discontinued.

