2.3.2. Risk Assessment

Table 2: Risk Assessment

| Potential Risk of Clinical Significance | Summary of Data/Rationale for Risk | Mitigation Strategy |
|---|--|---|
| ILD/pneumonitis | There is an identified increased susceptibility to ILD/pneumonitis. Please refer to the lerociclib IB and DSUR for full details. | ILD appears to be a rare side effect of CDK4/6 inhibitor therapy. While there are no known risk factors for the development of ILD, participants who demonstrate symptoms related to pneumonitis (cough, dyspnea, chest pain, fever) should be promptly evaluated and treated effectively. Holding of lerociclib is necessary if there is clinical concern for pneumonitis. Participants may require steroid administration, as well. |
| Febrile neutropenia | There is a small risk of the development of febrile neutropenia. | If a participant is suspected of febrile neutropenia, lerociclib should be held. Neutropenia from CDK4/6 inhibitors does not respond to G-CSF. Supportive care should be provided as clinically indicated while the participant's counts recover. Following the resolution of febrile neutropenia, a participant may continue lerociclib, with appropriate dose reduction as necessary. |
| Lerociclib | | |
| Neutropenia | Lerociclib has been demonstrated to cause a decline in neutrophil counts over the first 4–5 weeks of therapy. | Complications of neutropenia (infection, febrile neutropenia) are uncommon, and participants will be screened for potential complications at all study visits. |
| Gastrointestinal tolerability | Participants exposed to lerociclib commonly experienced transient diarrhea and nausea. | None of the TEAEs of diarrhea or nausea have been shown to be of Grade 4 or higher severity. Gastrointestinal side effects do respond to supportive therapy (anti-emetics, antidiarrheals). |

Table 2: Risk Assessment (Continued)

| Potential Risk of Clinical Significance | Summary of Data/Rationale for Risk | Mitigation Strategy |
|---|--|--|
| ILD/pneumonitis | Four of 140 study participants (2.9%) were diagnosed with ILD/pneumonitis based on clinical history and diagnostic findings. | Two study participants required hospitalization with no intensive care support. There were no fatal cases. There were no reports of ILD/pneumonitis in healthy participants. Caution should be taken for any participants with upper respiratory infection symptoms or dyspnea/hypoxemia. There should be a low threshold to re-image in such cases. |
| Study Procedures | | |

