6.5. Dose Modification

6.5.1. Lerociclib

A participant may temporarily discontinue from study treatment with lerociclib for a duration of up to 14 days, for any reason. However, any such temporary discontinuations must be reported to the Medical Monitor. Refer to Section [7.1.2](#) for details.

This protocol allows some alteration from the currently outlined lerociclib dosing schedule, but the maximum daily dose will not exceed 300 mg. Dose adjustments of lerociclib for toxicities are to be made according to the organ system showing the greatest degree of drug-related toxicity. Toxicities will be graded using NCI CTCAE v5.0.

No more than 2 lerociclib dose-level reductions in total are allowed for any participant. Toxicity that requires dose-level reduction more than twice will lead to permanent discontinuation of lerociclib dosing for the individual participant. No lerociclib dose re-escalations are allowed if the dose reduction was due to a lerociclib-related toxicity.

In cases where the relationship to lerociclib is unclear, the Investigator may re-challenge the participant after discussion with the Medical Monitor.

Dose reduction will only be performed if the symptom(s) is (are) related to lerociclib in the opinion of the Investigator and not related to the underlying disease. The dose level reductions below will be utilized for the purpose of lerociclib modifications for toxicities.

Table 5: Lerociclib Dose Modifications

| Dose Level | Lerociclib Dose |
|-----------------------|-----------------------|
| Starting dose | 150 mg BID |
| First dose reduction | 100 mg BID |
| Second dose reduction | 50 mg QAM, 100 mg QPM |

BID = twice daily; QAM = once every morning; QPM = once every evening.

An off-drug period of up to 14 days is permitted to allow recovery from any toxicity in order to meet the continuation criteria.

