7.1.2. Temporary Discontinuation of a Participant from Study Treatment

A participant may temporarily discontinue from study treatment for a duration of up to 14 days, for any reason. However, any such temporary discontinuations must be reported to the Medical Monitor and study assessments must continue as specified in the SoA.

If the IMP (lerociclib) is temporarily discontinued for any study participant, it may be restarted within the aforementioned 14-day period under the discretion of the Investigator with notice to the Medical Monitor. Beyond a duration of 14 days, the participant may not re-start lerociclib therapy and will be removed from the study.

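### The dosing rule for non-hematologic toxicity has no exception for pneumonitis, although the protocol's own risk table requires a hold on clinical concern at any grade, and restart within 14 days is stated at two approval levels

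*Protocol*

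**What the plan says.** **Protocol section 2.3.2, Table 2.** For ILD/pneumonitis the mitigation column states: "Holding of lerociclib is necessary if there is clinical concern for pneumonitis". No grade is attached, and nothing is said about when or at what dose treatment may restart. The continued table reports 4 of 140 participants (2.9%) with ILD/pneumonitis and adds: "Two study participants required hospitalization with no intensive care support. There were no fatal cases".

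**Protocol section 6.5.1.2.** The rule for every non-hematologic toxicity reads: "For any non-hematologic toxicity of Grade ≥ 3 severity that persists despite optimal medical treatment, withhold treatment with lerociclib", and continues "until symptoms resolve to Grade ≤ 2 severity (if not considered a safety risk for the participant"). Resumption is at the next-lower dose level. On approval: "If the treatment interruption duration is > 14 days, approval from the Medical Monitor will be needed to resume treatment".

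**Protocol section 6.5.1.** Lerociclib may be stopped for up to 14 days for any reason. "However, any such temporary discontinuations must be reported to the Medical Monitor". Where the link to lerociclib is unclear, re-challenge follows a discussion with the Medical Monitor.

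**Protocol sections 7.1.2 and 7.1.3.** After a temporary stop of lerociclib, "it may be restarted within the aforementioned 14-day period under the discretion of the Investigator with notice to the Medical Monitor". Section 7.1.3 instead requires the Medical Monitor's explicit permission for re-challenge. After a stop for toxicity, the Investigator must also confirm that the event is resolving, to Grade 2 or better.

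Section 6.5 names neither pneumonitis nor ILD, and does not refer to Table 2.

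**The concern.** When a toxicity occurs, a site turns to section 6.5. For lung toxicity that section gives a higher threshold for stopping than Table 2 does: Grade 3 or above that persists despite treatment, against clinical concern at any grade. Followed alone, it requires no hold for a suspected, Grade 1 or Grade 2 pneumonitis.

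The sponsor did carry a comparable risk across. Table 2 also asks for a hold on suspected febrile neutropenia, and Table 6 has a row for Grade 3 or higher neutropenia with infection or fever, giving a hold, a recovery threshold and a resumption dose. Pneumonitis has no such entry.

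At stake is consistent handling of a recognised toxicity. Section 2.3 lists ILD/pneumonitis among the anticipated toxicities, and SAP section 4.9.1.3 makes pneumonitis and ILD two of its three adverse events of special interest. Section 4.3 reports that the only lerociclib-related SAE at 150 mg BID was a Grade 2 pneumonitis, a grade at which 6.5.1.2 requires no hold. Participants with the same lung event could be stopped, and restarted, under different conditions at different sites.

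**Working it through.** The point rests on comparing texts. The arithmetic only shows how often the rules would be needed.

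**1. When must lerociclib be held?**

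| Event | Table 2 | Section 6.5.1.2 |
|---|---|---|
| Suspected pneumonitis, ungraded | Hold | No hold required |
| Grade 1 or 2 | Hold | No hold required |
| Grade 3 or above, not persisting despite treatment | Hold | No hold required |
| Grade 3 or above, persisting | Hold | Hold |

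The two differ in every row but the last. They do not conflict, because 6.5.1 permits a stop for any reason and 6.5.1.2 nowhere forbids one.

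**2. What governs restart?**

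- *Hold begun at persistent Grade 3 or above.* Section 6.5.1.2 applies: Grade 2 or below, not considered a safety risk, next-lower dose.
- *Hold begun under Table 2 at Grade 1 or 2.* The Grade 2 clause of 6.5.1.2 ends holds that began at Grade 3 or above, so it does not govern this one. That leaves the generic rules: 7.1.2, 7.1.3 and, where causality is unclear, the discussion required by 6.5.1. None is specific to pneumonitis, and none gives a restart dose for this case.

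**3. Whose approval is needed within 14 days?** Under 7.1.2, the Investigator decides and gives notice. Under 7.1.3, the Medical Monitor must give explicit permission. Section 7.1.3 expressly covers stops for toxicity and can be read as the more specific rule, but the protocol does not say that it overrides 7.1.2.

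**4. After 14 days.** A neighbouring point: 6.5.1.2 allows resumption with approval, whereas 7.1.2 says "Beyond a duration of 14 days, the participant may not re-start lerociclib therapy and will be removed from the study".

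**5. How often would this arise?** Inputs: 4 of 140 with ILD/pneumonitis, of whom 2 were hospitalized (Table 2); about 100 participants planned (section 9.4).

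- Reproducing the protocol's figure: 4/140 = 2.86%, which rounds to the stated 2.9%.
- Exact (Clopper-Pearson) 95% interval: lower limit is the 2.5% point of Beta(4, 137) = 0.78%; upper limit is the 97.5% point of Beta(5, 136) = 7.15%.
- Expected cases in 100: 100 × 0.0286 = 2.9 (0.8 to 7.2).
- Chance of at least one case: 1 − (1 − p)^100 = 94.5% at p = 2.86% (54.5% at 0.78%; 99.9% at 7.15%).
- Hospitalized: 2/140 = 1.43%, interval 0.17% to 5.07%; expected in 100 = 1.4 (0.2 to 5.1).

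**The case against.** The best reply is that nothing is actually missing. Table 2 is part of the protocol, section 10.1.11 requires the protocol to be followed exactly, and a site can hold under Table 2 without breaching 6.5. Generic safeguards also bind. Temporary stops are reported to the Medical Monitor. Re-challenge of an unclear case needs discussion (6.5.1), and re-challenge after toxicity needs explicit permission (7.1.3). An event judged an unacceptable risk ends treatment (7.1.1). Immediate safety concerns go to the sponsor (section 8). The Investigator's Brochure and DSUR, to which Table 2 refers, may hold management guidance; they were not available to check.

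Most of this stands, and it rules out two stronger readings that a reader might infer.

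- *That the protocol contradicts itself or tells sites to dose through low-grade pneumonitis.* It does not. A rule that requires a hold at Grade 3 does not forbid one below it.
- *That a Grade 2 pneumonitis qualifies for restart from onset.* It does not. The Grade 2 clause in 6.5.1.2 belongs to holds begun at Grade 3 or above and carries a safety-risk proviso. Under 7.1.3 the event must be resolving, which a case at onset is not.

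What the reply does not remove: the mandatory hold is absent from the dosing section, notice and permission are both stated for the same interval, and no pneumonitis-specific restart condition or dose exists for a hold begun at Grade 1 or 2.

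**Conclusion.** The point holds as a participant-safety clarification of modest severity. For lung toxicity, section 6.5.1.2 read alone is less protective than Table 2, and the restart rules leave the approval level open within 14 days. No endpoint or analysis is affected.

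The expected 3 or so cases assume that the earlier rate carries over. Table 2 does not say which doses or combinations lie behind the 140. Earlier patient studies included doses up to 650 mg once daily (section 4.3) and a combination with osimertinib (section 2.2.2). The figures count every case. It would be wrong to read the 94.5% as the chance of a mishandled case; the documents give no basis for estimating that. Table 2 reports no intensive care and no deaths.

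**What to change.** Add a short paragraph to section 6.5.1.2 that:

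1. exempts suspected or confirmed ILD/pneumonitis from the generic rule (hold at Grade 3 or above, resume at Grade 2 or below);
2. repeats the Table 2 hold on clinical concern, at any grade;
3. allows restart only once the concern has been excluded or the event has resolved, and says that Grade 2 alone is not enough;
4. makes 7.1.3, with the Medical Monitor's explicit permission, govern every restart after such a hold, including holds of 14 days or less;
5. cross-refers to Table 2 and 7.1.3.

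The sponsor should also name the restart dose in the same paragraph, and could settle the difference between 6.5.1.2 and 7.1.2 after 14 days in the same amendment.

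**Cost.** A protocol amendment; if classed as substantial, it needs the approvals described in section 10.1.1. Beyond that, there would be some extra precautionary holds at sites that would otherwise have worked from section 6.5 alone, and one Medical Monitor approval per restart. No new visits or procedures are needed.

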6.5.2. Letrozole, Fulvestrant, and Goserelin

Dose modification of letrozole, fulvestrant, or goserelin is not allowed during the study for any participant.

6.6. Missed Doses

In the event that a participant misses a dose of lerociclib, that participant should resume lerociclib at the next scheduled dose. No attempts should be made to make up for missed doses.

6.7. Continued Access to Lerociclib after the End of the Study

Participants who have completed all scheduled clinical study visits and continue to show benefit from lerociclib will be eligible to participate in a rollover study for continued access to lerociclib.

6.8. Definition and Treatment of Overdose

Note: “Overdose” and “noncompliance” are not interchangeable in this protocol. This section refers specifically to overdose in the context of a clinical study. Refer to Section 6.4 for information regarding study intervention compliance.

In the context of a clinical study, an overdose is any dose which exceeds the daily dose that is defined in the clinical study protocol.

In this study, if an overdose on any study intervention, including the IMP (lerociclib), occurs in the course of the study, then the Investigator or other site personnel shall inform the appropriate Sponsor representatives immediately, or no later than 24 hours of first becoming aware of it. The designated Sponsor representative shall work with the Investigator to ensure that all relevant information is provided to the Sponsor or designee.

For overdoses associated with an AE/SAE, the standard reporting timelines apply.

There is no specific treatment in the event of lerociclib overdose, and symptoms of overdose are not established. In the event of an overdose, the Investigator should hold lerociclib, follow general supportive measures, and treat symptomatically.

6.9. Prior and Concomitant Therapy or Procedures

The Investigator or qualified designee will review prior medication use, including prescription medications, over-the-counter preparations, growth factors, blood products, and parenteral nutrition, and record prior medications taken by the participant within 14 days prior to the first day of Screening Visit.

The Investigator or qualified designee will record medication, if any, taken by the participant during the study through the last study visit.

Documentation will include information regarding start and stop dates, dose(s), and reasons for the medication use.

The Medical Monitor should be contacted if there are any questions regarding concomitant or prior therapy.

Administration of other concomitant, non-protocol, anticancer therapies prior to disease progression is not permitted while receiving IMP (lerociclib) during the study (not including EOT/ED, Safety Follow-up, and long-term Survival Follow-up).

Administration of other concomitant investigational agents for any indication is not permitted while receiving IMP (lerociclib) during the study (not including long-term Survival Follow-up).

Granulocyte colony-stimulating factor may not be used during the first 4 weeks on study. After the first 4 weeks on study, the Investigator must contact the Medical Monitor if they believe that G-CSF use is clinically indicated for a study participant that has temporarily stopped lerociclib and is experiencing prolonged neutropenia (more than 10 days after the cessation of lerociclib).

Use of a 5-HT₃ antagonist may be used on an as needed basis but should be used with caution at the Investigator's discretion. Symptomatic management of diarrhea with loperamide, when required, should commence in a timely fashion. Sites should ensure that participants are adequately informed on the proper use of loperamide.

CYP3A4 Substrates

Lerociclib has the potential to inhibit CYP3A4/5 in both a competitive and time-dependent manner based on in vitro studies.

Using the FDA-recommended model-based predictions in the guidance for drug interaction studies ([FDA 2020](#)), lerociclib has the potential to significantly inhibit CYP3A4 in the gut and thus may have a clinically significant effect on orally administered CYP3A4 substrates with a narrow therapeutic index, and such drugs are prohibited during participation in this study (beginning 14 days prior to the first dose of lerociclib, until 14 days after the last dose of lerociclib).

- Prohibited, orally administered CYP3A substrates with a narrow therapeutic index:
 - astemizole, cisapride, cyclosporine, dihydroergotamine, ergotamine, everolimus, pimozone, quinidine, sirolimus, and tacrolimus

- **Monitor frequently for adverse reactions** with concomitant use of drugs that are orally administered CYP3A substrate drugs, with consideration of dose reduction of the substrate if clinical signs and symptoms of toxicity emerge (eg, muscle aches with 3-hydroxy-3-methylglutaryl coenzyme A reductase inhibitors).

The model-based calculation for inhibition of CYP3A4 in the liver predicts a marginal inhibitory effect by lerociclib and therefore the likelihood of a clinically significant drug interaction for CYP3A substrates administered via routes other than oral (eg, IV, transdermal, inhalation, etc) is low.

- **Caution should be exercised** with concurrent use of non-orally administered CYP3A substrates with a narrow therapeutic index with consideration of dose reduction of the substrate if clinical signs and symptoms of toxicity emerge (eg, increased somnolence with transdermal fentanyl or IV midazolam).

CYP3A4 Inhibitors and Inducers

Lerociclib is a substrate for CYP3A4, although the extent of metabolism by CYP3A4 is expected to be low in humans since the in vitro clearance of lerociclib in human liver microsomes and hepatocytes was low. Lerociclib exposure may be altered by concomitant use of drugs that are strong CYP3A inhibitors or inducers. Concomitant use of drugs that are strong or moderate CYP3A inducers is to be avoided.

- Prohibited drugs that are strong or moderate CYP3A inducers include the following:
 - phenytoin, rifampin, carbamazepine, St John's Wort, bosentan, modafinil, and nafcillin
- **Monitor frequently for adverse reactions** with concomitant use of drugs that are strong CYP3A inhibitors (eg, grapefruit juice, aprepitant, clarithromycin, itraconazole, ketoconazole, nefazodone, posaconazole, telithromycin, verapamil, and voriconazole).

CYP2C8 Inhibitors and Inducers

Lerociclib is a substrate for CYP2C8, although the extent of metabolism by CYP2C8 is expected to be low in humans since the in vitro clearance of lerociclib in human liver microsomes and hepatocytes was low. Lerociclib exposure may be altered by concomitant use of drugs that are strong CYP2C8 inhibitors or inducers.

- **Caution should be exercised** with concomitant use of drugs that are strong inhibitors of CYP2C8 (eg, gemfibrozil, quercetin, sulfapyrazone, trimethoprim, and nicardipine).
- **Monitor for efficacy** with concomitant use of drugs that are strong or moderate inducers of CYP2C8 (eg, rifampin, phenobarbital, and carbamazepine).

Bisphosphonates and Denosumab

Bisphosphonates and denosumab for the treatment of osteoporosis or management of existing bone metastases may be continued for participants who have been receiving them at a stable dose for at least 14 days prior to first dose of lerociclib.

However, the need to initiate or increase the dose of these therapies during the study will be considered as indicative of disease progression leading to the discontinuation of participant from the study unless disease progression can be completely ruled out and the exact reason for the use of these therapies is clearly documented in the participant's source documentation. Such cases must be discussed with the Medical Monitor first.

Medications Not Recommended

Chronic immunosuppressive therapies should be avoided, including systemic corticosteroids. Steroids given for physiological replacement, as anti-emetics or by inhalation, as well as short course of oral/topical steroids given for allergic reactions or asthma flares are allowed.

Any use of systemic corticosteroids for reasons other than those mentioned above shall be discussed with the Medical Monitor prior to use.

The use of herbal medicine is not recommended.

Additional Cautions

Lerociclib inhibited P-gp, BCRP, MATE1, MATE2-K, and OCT1 and OCT2 membrane transporters and therefore caution should be exercised with concomitant use of drugs that are substrates for these transporters. MATE2-K is involved with tubular secretion of creatinine and inhibition of MATE2-K by lerociclib may cause an increase in serum creatinine levels unrelated to true changes in renal function.

Lerociclib is a substrate and inhibitor of P-gp and BCRP efflux transporters. Lerociclib exposure may be altered by concomitant use of drugs that are strong inhibitors or inducers of P-gp or BCRP.

- Monitor for adverse reactions when co-administering medications that are strong inhibitors of P-gp and BCRP.

Concomitant Radiotherapy and Surgery

Palliative radiotherapy may be permitted for the treatment of painful bony lesions provided that the lesions were known to be present at the time of study entry and the Investigator clearly documents that the need for palliative radiotherapy is not indicative of disease progression.

Approval from the Medical Monitor should be obtained prior to any surgery or start of alternative therapy that are not considered palliative.

Any diagnostic, therapeutic, or surgical procedures performed while the participant is receiving IMP (lerociclib) during the study period will be documented. Documentation will include information regarding the date(s), indication(s), description of the procedure(s), and any clinical or pathological findings.

Medications will be coded using the WHO Drug Dictionary.

